6.13.3 Immediately Reportable AEs

The investigator must report any SAE to the sponsor or its representative immediately after the investigator becomes aware of the event. An SAE form should be completed and sent to the sponsor within 24 hours of knowledge of the event.

Non-serious events that require discontinuation of investigational product (including laboratory abnormalities) should be reported to the sponsor within 3 working days. The CRF AE form should be completed and sent to the sponsor.

Subjects experiencing an SAE should be followed clinically until their health has returned to baseline status or no further improvement in condition can be expected with further care. It is expected that the investigator will provide or arrange appropriate supportive care for the subject.

6.13.4 Pregnancy

WOCBP who are sexually active must use an effective method of birth control during the course of the study, in a manner such that risk of failure is minimized.

Before enrolling WOCBP in this clinical trial, investigators must review guidelines about study participation for WOCBP. The topics should generally include:

- 1. General information
- 2. Informed consent form
- 3. Pregnancy prevention information
- 4. Drug interactions with hormonal contraceptives.
- 5. Contraceptives in current use.
- 6. Guidelines for the follow-up of a reported pregnancy.

Prior to study enrollment, WOCBP must be advised of the importance of avoiding pregnancy during trial participation and the potential risk factors for an unintentional pregnancy. The subject must sign an informed consent form stating the above-mentioned risk factors and that the consequences were discussed with her.

During the study, all WOCBP should be instructed to contact the investigator immediately if they suspect they might be pregnant (e.g. missed or late menstrual cycle).

If a subject or investigator suspects that the subject may be pregnant prior to investigational product administration, the investigational product administration must be withheld until the results of serum pregnancy tests are available. If the pregnancy is confirmed, the subject must not receive the investigational product and must not be enrolled or remain in the study. If pregnancy is suspected while the subject is receiving study treatment, the investigational product must be withheld immediately until the result of the pregnancy test is known. If pregnancy is confirmed, the investigational product will be permanently discontinued and the

subject will be withdrawn from the trial. (Exceptions to study discontinuation may be considered for life-threatening conditions only after consultations with a sponsor Medical Monitor or designated personnel.) The investigator must notify the Medical Monitor within 3 working days of any female subject who becomes pregnant. This reporting requirement will continue until 4 weeks after the last investigational product exposure.

The investigator must record the event on the Pregnancy Surveillance Form and forward it to sponsor's clinical or designated personnel.

Protocol required procedures for study discontinuation and follow-up must be performed on the subject unless contraindicated by pregnancy (*e.g.*, x-ray studies). Other appropriate pregnancy follow-up procedures should be considered if indicated. In addition, the investigator must report to the sponsor, on the appropriate Pregnancy Surveillance Form, follow-up information regarding the course of the pregnancy, including perinatal and neonatal outcome. Infants will be followed for a minimum of six months.

6.13.5 Procedure for Breaking the Blind

As indicated in Section 5.5 above, the sponsor, medical monitor, study coordinators, pharmacists, study subjects, and the CEC members will be blinded to the treatment assignment during the study period. The investigator should also remain blinded to the subject treatment during the entire study unless knowledge of the subject's treatment is required for clinical care and safety. The Emergency Code Break module in the IWRS is used for such situations. The investigator must confirm the intention to unblind the subject's treatment to obtain the dose information in IWRS. Upon completion of the unblinding, the system will send an alert to designated study team members that an unblinding event has occurred. Documentation of breaking the blind should be recorded in the subject's medical record with the date and time the blind was broken, and the names of the personnel requesting and authorizing unblinding. The treatment assignment will continue to be withheld from the CEC members until all phase 3 studies are completed.

6.13.6 Follow-up of Non-Serious AEs

Non-serious AEs that are identified on the last scheduled contact must be recorded in the AE CRF with the current status noted. All non-serious events that are ongoing at the time will be recorded as ongoing in the CRF.

6.13.7 Follow-up of Post-Study SAEs

SAEs that are identified on the last scheduled contact must be recorded on the AE CRF page and reported to the sponsor according to the reporting procedures outlined in Section 6.13.3. These may include unresolved previously reported SAEs, or new SAEs. The investigator should follow these SAEs until the events are resolved, or the subject is lost to follow-up. Resolution means the subject has returned to the baseline state of health, or the investigator does not expect any further improvement or worsening of the subject's condition. The investigator should continue to report any significant follow-up information to the sponsor until the event has been resolved. Any new SAEs reported by the subject to the investigator that occur after the last scheduled contact, and are determined by the investigator to be reasonably associated with the use of the investigational product, should be reported to the sponsor or designated personnel. This may include SAEs that are captured on follow-up telephone contact or at any other time point after the defined study period (i.e., up to last scheduled contact). The investigator should follow SAEs identified after the last scheduled contact until the events are resolved, or the subject is lost to follow-up. The investigator should continue to report any significant follow-up information to the sponsor until the event has been resolved. This study requires that subjects be actively monitored for SAEs for at least 4 weeks after the last treatment.

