3.2.2 Treatment Period

The treatment period will start at randomization (Visit V6) and end after 24 weeks. At the start of the treatment period, each subject will be provided investigational product, dosing instructions, and glycemic control diary in which to record symptoms related to any hyper- or hypoglycemic events as well as information related to the occurrence of such events. Subjects with uncontrolled hyperglycemia based on blood glucose levels may receive additional approved anti-diabetic rescue medications (see Prescription of Rescue Medication below). Bexagliflozin tablets will be orally administered in the morning with 250 mL of water prior to eating or drinking.

Each subject will participate in a telephone consultation at week 2 (Visit V7) for safety monitoring. Each subject will be instructed to return to the clinic at weeks 6, 12, 18, and 24 (Visits V8, V9, V10, V11, respectively) for efficacy assessment and safety monitoring, including review of adverse events and concomitant medication, evaluation of vital signs, electrocardiogram (ECG), and a physical examination, and for a blood draw and urine

collection for clinical laboratory. On the day of the clinic visit, a fasting time of approximately 10 hours must be confirmed prior to blood draw.

To minimize the effect of missing values on data analysis and study outcome interpretation, considerable effort will be made to prevent missing data, to train site staff to encourage study subject participation and to remain vigilant to signs of non-compliance, to remain in contact with study subjects who have withdrawn from the study to collect as nearly complete a data set as is feasible, and to determine all reasons for missing data.

Subjects will return to the clinic for a follow-up exit visit at week 26 (Visit V12) or two weeks after the last dose of investigational product if the subject terminates prior to week 24. Following the exit visit, subjects will be advised to see their primary physician and resume treatment to control their diabetes. The duration of participation for each subject can be up to 37 weeks depending on prior treatment status.

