3.4 Study Duration and Dates

Potential subjects will be screened within 3 weeks of the start of wash-out or run-in period. Eligible subjects who are taking a background OHA and sign the informed consent will start a 6-week wash-out period, followed by a 2-week single-blind placebo run-in period. Eligible subjects who are treatment naïve and sign the informed consent form will immediately start the 2-week single blind placebo run-in period. Subjects who remain eligible at the end of the run-in period will receive 24 weeks of treatment. All subjects who are randomized will be followed for 2 weeks after the last dose of investigational product. The overall study duration from screening to follow-up could be a maximum of 37 weeks. The duration of the overall study depends on the rate of subject accrual. For details of the schedule and nature of the investigations, see the Schedule of Events in Appendix 1

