3.4. BRIEF DESCRIPTION

THR-1442-C-450 is a multi-center, randomized, double-blind, placebo-controlled, parallel-group study. It is designed to compare the efficacy and safety of once daily oral administration of bexagliflozin tablets, 20 mg to bexagliflozin tablets, placebo, in treatment-naïve type 2 diabetic subjects or subjects previously treated with no more than one oral hypoglycemic agent (OHA).

All eligible subjects will start a 2 week placebo run-in period. Subjects who miss no more than one dose of the run-in medication, have fasting blood glucose values \geq 250 mg/dL on no more than two consecutive days, and who, at the baseline visit (Visit V5), have an HbA1c level between 7 and 10.5% and a fasting glucose level < 250 mg/dL will be eligible for randomization.

Approximately 210 subjects will be randomly assigned to receive oral bexagliflozin tablets, 20 mg or placebo, in a 2:1 ratio once daily for 24 weeks in an out-patient setting. Subjects with uncontrolled hyperglycemia based on blood glucose levels may receive additional approved anti-diabetic medications. Treatment group assignment at the start of the treatment period will be stratified by HbA1c level at the start of the run-in period (7.0 to 8.5% or 8.6 to 10.5%) and background anti-diabetes treatment status (treatment naïve or not).

Each subject will be contacted by telephone at week 2 (Visit V7) for safety monitoring and will be instructed to return to the clinic at weeks 6, 12, 18, and 24 (Visits V8, V9, V10, V11) for efficacy assessment and safety monitoring. Subjects will return to the clinic for a follow-up visit at week 26 or two weeks after the last dose of investigational product if the subject terminates prior to week 24 (Visit V12).

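### No scheduled contact implements the required four weeks of active SAE monitoring after last treatment: the schedule ends two weeks after the last dose

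*Protocol*

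**What the plan says.** **The requirement.** Protocol 6.13.7 closes with "This study requires that subjects be actively monitored for SAEs for at least 4 weeks after the last treatment". SAP 9.3 repeats that sentence word for word.

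**The schedule.** Protocol 3.4 says "All subjects who are randomized will be followed for 2 weeks after the last dose of investigational product". Protocol 3.2.2 sets the final visit, V12, accordingly: week 26 for completers, or a fortnight past the final dose for those who stop before week 24. Protocol 3.1 and SAP 3.4 agree. Neither Protocol Appendix 1 nor SAP Table 1 has a column after V12. Protocol 3.4 adds that the duration from screening to follow-up "could be a maximum of 37 weeks".

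**After the last scheduled contact.** Protocol 6.13.7 and SAP 9.3 ask for a new SAE to be passed to the sponsor when the subject reports it and the investigator considers it plausibly linked to the product. Both mention telephone follow-up as one way such an event might come to light, but give it no date and no place in the schedule. SAP 9.3 also runs AE collection from consent only to the last scheduled contact.

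**The concern.** The requirement calls for active monitoring over a minimum of four weeks, and the schedule provides a contact at two weeks and nothing later. The rule for the remaining time is close to the opposite of active: it waits for the subject to volunteer the event and then admits it only on a causality judgement. SAP 9.3 holds both positions within one paragraph.

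What is at stake is the completeness and comparability of SAE data late in follow-up. A site that works from Appendix 1 departs from 6.13.7. A site that telephones at week 28 collects events that other sites do not. The treatment-emergent definition in Protocol 9.7.1 and SAP 9.3 has no end date, so an SAE at week 27 would enter the tables at one site and never be recorded at another. Protocol 9.9 and SAP 2.2 time the final analysis to the end of follow-up, which is the period the documents leave unsettled.

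**Working it through.** **1. Inputs**
- Screening: "Potential subjects will be screened within 3 weeks of the start of wash-out or run-in period" (Protocol 3.4), so 3 weeks.
- Wash-out and run-in: subjects on a prior agent "will start a 6-week wash-out period, followed by a 2-week single-blind placebo run-in period" (Protocol 3.4), so 6 + 2 weeks.
- Treatment: "Subjects who remain eligible at the end of the run-in period will receive 24 weeks of treatment" (Protocol 3.4), so 24 weeks.
- Follow-up: 2 weeks after last dose (Protocol 3.4).
- Required active SAE monitoring: at least 4 weeks, or 28 days (Protocol 6.13.7, SAP 9.3).
- Visit window: ±3 days for every visit except V6 (Protocol 7, SAP 3.9).
- Planned randomised: about 210 (Protocol 9.2, SAP 3.6).

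**2. Reproduce the stated maximum duration**

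3 + 6 + 2 + 24 + 2 = 37 weeks. This matches the span of Appendix 1, from week −11 to week 26 (11 + 26 = 37). The stated figure therefore rests on two weeks of follow-up.

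**3. Scheduled coverage against the requirement**

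Taking the last dose at week 24:

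| V12 timing | Days after last dose | Shortfall against 28 |
|---|---|---|
| 3 days early | 14 − 3 = 11 | 17 |
| Nominal | 14 | 14 |
| 3 days late | 14 + 3 = 17 | 11 |

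V11 has its own window. If the last dose moved 3 days earlier with V11 and V12 fell 3 days late, the interval would be 14 + 3 + 3 = 20 days, still 8 short. No use of the windows reaches 28 days.

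**4. Who is affected**
- Completers: last dose at about week 24, last scheduled contact at week 26.
- Early terminators whose V12 is set two weeks after the last dose: the same gap.
- Subjects who stop the product but keep attending visits: possibly observed well beyond four weeks. Protocol 6.13.13, for example, continues follow-up for cardiovascular events through the study after the product is permanently withdrawn. The gap need not apply to them.

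**5. Size of the uncovered time**

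Ceiling at nominal timing: 210 × 2/52 = 8.1 patient-years. Randomisation to week 26 for the same 210 subjects: 210 × 26/52 = 105 patient-years. Ratio: 8.1/105 = 7.7%.

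If every V12 sat at one edge of its window, the ceiling would move to 210 × 11/364 = 6.3 or 210 × 17/364 = 9.8 patient-years.

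**6. Duration if a contact were added**

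A contact four weeks after the last dose would fall at week 24 + 4 = 28 for a completer. The maximum would become 3 + 6 + 2 + 24 + 4 = 39 weeks, provided that contact counts as part of the study.

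**The case against.** The best defence is that the protocol separates the scheduled study period from surveillance afterwards. Section 6.13.7 is about post-study SAEs, defines the study period as ending at the last scheduled contact, and foresees events learned of by telephone later. On that reading the four-week sentence is itself an instruction to sites, and nothing prevents an unscheduled call. A reader might infer that the monitoring is impossible, or that V12 is the last contact of any kind. The documents do not support either inference. What survives is narrower: the instruction has no timing, no schedule entry and no form of contact, and the rule beside it admits only volunteered events judged related.

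The same defence weakens the duration argument. Thirty-seven weeks describes screening to scheduled follow-up and can coexist with a longer surveillance period outside it. The figure shows what the schedule was built on; it does not prove a contradiction, and 39 weeks is conditional.

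A reader might also infer that the MACE+ contribution would cover a shorter period than the documents claim. That does not follow. Protocol 6.13.13 follows cardiovascular events for the duration of the study, and no passage promises a four-week post-treatment period for MACE+. The four-week sentence concerns SAEs. Because MACE reports are also captured as SAEs, a late event could go unrecorded, but no stated MACE+ period is broken.

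Finally, the plan expects about 10% early termination, the uncovered time is off treatment, and the documents give no SAE rate. Patient-years of gap therefore cannot be turned into a number of lost events.

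**Conclusion.** The point stands as an internal inconsistency: both documents state a four-week active SAE monitoring requirement that no scheduled contact implements. The nominal shortfall is 14 days, or 11 to 17 days with the V12 window and the last dose at week 24. For completers, and for early terminators seen two weeks after the last dose, SAE capture in roughly weeks 2 to 4 is passive and filtered by relatedness if sites follow the schedule as written.

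The 8.1 patient-years is a ceiling, not an estimate. It assumes that all 210 subjects are affected, that each attends V12 exactly 14 days after the last dose, and that no site makes an unscheduled call. It measures time without scheduled contact, not events lost.

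The primary and key secondary analyses, the sample size and the multiplicity scheme are unaffected. The point merits correction because it concerns a safety commitment that sites cannot apply uniformly from the text they have. Which monitoring period should apply is for the sponsor to settle.

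**What to change.** Reconcile Protocol 6.13.7 and SAP 9.3 with Protocol 3.1, 3.2.2, 3.4 and Appendix 1, and with SAP 3.4 and Table 1. There are two ways to do it:

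- **Restate the period.** Make the active SAE monitoring period equal to the scheduled follow-up in both documents. The present rule for events after the last scheduled contact can then stand as passive reporting beyond that period.
- **Deliver the period.** Add a contact to Appendix 1 and SAP Table 1 that reaches the end of the stated period, and write an SAE collection rule to match, so that capture up to that contact depends neither on the subject volunteering the event nor on relatedness. Align the end of collection in SAP 9.3, and revise the 37-week maximum if the contact counts as part of the study.

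The sponsor chooses the period and uses the same figure throughout. The four-week pregnancy reporting period in Protocol 6.13.4 also has no scheduled contact behind it and should be checked in the same pass.

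The cost is an amendment to the wording of both documents, with IRB/IEC approval of the protocol change (Protocol 10.2) and possibly a consent revision (Protocol 10.4). If the longer period is kept, add one telephone contact per subject.

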6.13.8 Urinary Tract Infections (UTIs)

Events potentially representing UTIs, including cystitis, urethritis, pyelonephritis, or urosepsis, should be carefully evaluated and documentation of signs, symptoms, culture results for infectious agent, and treatment should be undertaken when appropriate.

The investigator should query the subject at every clinical visit for symptoms that may be related to a UTI and, if appropriate, document these events as symptomatic UTI in the CRF unless an alternative diagnosis is present. In addition, a clean catch urine sample will be obtained at all clinical visits and a urinalysis will be performed on that sample at every clinical visit. A positive urinalysis will be defined as one with detectable leukocyte esterase and/or nitrites (1+ or greater). If the subject reports symptoms consistent with a UTI or the urinalysis at the clinical site is positive, a urine culture will be performed in a designated laboratory. A positive urine culture will be defined as one with $\geq 10^5$ CFU of any species. The investigator may also perform a urine culture using local resources if necessary for clinical care.

6.13.9 Genital Mycotic Infections (GMIs)

The investigator will query the subjects for signs or symptoms that may represent a GMI at all clinic visits. GMIs will be diagnosed based on symptoms and, if appropriate, physical exam and laboratory findings. Investigators must exclude the possibility of sexually transmitted infections before diagnosing GMI. Diagnosis of GMIs must be documented in the CRF.

6.13.10 Hepatotoxicity

If plasma AST and/or ALT concentrations > 3 x ULN are detected, the investigator will record in the source documents the date corresponding to the date of the laboratory abnormality; the type, frequency, and dose of any concurrent medications or supplements taken by the subject within the 14 days of the detected abnormality; and any symptoms or change in physical exam that have occurred since the prior assessment. The investigator should perform additional laboratory and imaging tests to attempt to establish the cause of the AST and ALT elevations, including ruling out any potential contribution from bone or muscle etiologies.

Any clinically significant increase in hepatic enzymes and specifically any ALT or AST > 3 x ULN requires immediate repeat test within 48 to 72 hour to confirm the hepatic enzyme

elevation and should be repeated based on the clinical situation at least every 96 hour (4 days) until ALT and AST return to < 2.5 x ULN. Study medication should be stopped and the event should be reported as a laboratory AE within the CRF if the enzyme elevation is confirmed or worsening.

Hepatotoxicity will be diagnosed and entered as an AE should any of the following occur:

- ALT or AST $> 8 \times ULN$;
- ALT or AST > 3 x ULN and total bilirubin > 2 x ULN or INR > 1.5
- ALT or $AST > 3 \times ULN$ with the appearance of fatigue, nausea, vomiting, right upper quadrant pain or tenderness, fever, rash, and/or eosinophilia (> 5%).

In the event of hepatotoxicity, investigational product should be permanently discontinued. The investigator is encouraged to consult with the Medical Monitor regarding diagnostic evaluation for the hepatic enzyme elevations. Consultation with a hepatologist may also be appropriate in some circumstances.

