6.13.2 Eliciting and Reporting AEs

The investigator will periodically assess subjects for the occurrence of AEs after subject consents to participation in the study. To avoid bias in collecting information about AEs, the investigator should ask subjects the following question: "How have you felt since you were last checked?" All AEs (serious and non-serious) reported by the subject must be recorded in the source documents and CRFs provided by the sponsor.

It is the investigator's responsibility to review the results of all laboratory tests as they become available. For each abnormal laboratory test result the investigator needs to ascertain if this is a clinically significant change from baseline for that individual subject (this determination, however, does not necessarily need to be made the first time an abnormal value is observed. The investigator may repeat the laboratory test or request additional tests to verify the results of the original laboratory tests). If the laboratory value is determined to be a clinically significant and abnormal change from baseline for that subject, this is considered a laboratory AE.

Hypoglycemia is defined as any FPG or SMBG value \leq 70 mg/dL and should be documented based on the ADA hypoglycemia categories.

Any increase in liver function tests (AST, ALT, or bilirubin) greater than 3 times the ULN for the laboratory utilized will be considered a laboratory AE.

In addition, the sponsor's Medical Monitor and designated personnel must be notified immediately by telephone, email, or fax of any immediately reportable AEs (IRAE)

according to the procedure outlined below. Special attention should be paid to recording hospitalization and concomitant medications.

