9.3.3. AE of Special Interest

AE of special interest include urinary tract infection (UTI), genital mycotic infection (GMI), diuretic effects, hepatotoxicity, cardiovascular events, hypoglycemia, fracture, malignancy, hypersensitivity reactions, hypotensive episodes, acid-base disorders, renal failure events, and amputations. These AEs of special interest, except for cardiovascular events and amputations, will be prospectively identified based on the MedDRA PTs in the AEs log by a medical expert prior to the data base lock and unblinding of the individual subject treatment assignment. The list of AEs of special interest will be confirmed in a peer review process. Cardiovascular events, hypoglycemia events by severity, and amputations will be summarized separately.

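### Protocol 6.13.2 and 6.13.10 disagree on whether one unconfirmed ALT or AST above 3 x ULN is a laboratory AE, and the SAP's hepatic count rests on the AE log

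*Protocol*

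**What the plan says.** Protocol 6.13.2 sets a general rule: an AST, ALT or bilirubin increase "greater than 3 times the ULN for the laboratory utilized will be considered a laboratory AE". The paragraph before it lets the investigator repeat a test before judging clinical significance, a judgement that "does not necessarily need to be made the first time an abnormal value is observed". The 3 x ULN sentence stands apart and carries no such latitude.

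Protocol 6.13.10 has three relevant parts.
- Repeat test: "specifically any ALT or AST > 3 x ULN requires immediate repeat test within 48 to 72 hour to confirm" the elevation.
- Stop and report: "Study medication should be stopped and the event should be reported as a laboratory AE within the CRF if the enzyme elevation is confirmed". The same sentence also covers an elevation that is worsening.
- Hepatotoxicity: "Hepatotoxicity will be diagnosed and entered as an AE should any of the following occur". The list is ALT or AST above 8 x ULN; above 3 x ULN with total bilirubin above 2 x ULN or INR above 1.5; or above 3 x ULN with listed symptoms, rash or eosinophilia. Then: "In the event of hepatotoxicity, investigational product should be permanently discontinued".

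On counting, SAP 9.3.3 says that events of special interest other than cardiovascular events and amputations "will be prospectively identified based on the MedDRA PTs in the AEs log", by a medical expert before database lock and unblinding. Protocol 9.7.2 takes the same approach. SAP 9.3.3.1 reports these events as numbers, percentages and rates per 100 patient-years.

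**The concern.** Two sites with the same laboratory result can make different entries. One follows 6.13.2 and logs the first value above 3 x ULN as an AE. The other follows 6.13.10, repeats the test, sees it fall, and logs nothing. Both are following the protocol.

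This matters for the analysis because the AE log is the source for the hepatotoxicity count. An event that is not logged cannot be found by a review of preferred terms.

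The wording on stopping raises a lesser problem. Where a first value already meets a hepatotoxicity criterion, 6.13.10 gives both a repeat-test step and a permanent discontinuation, without saying how they are ordered. It also does not say whether the stop for a confirmed isolated elevation is temporary or permanent. Two planned items depend on this: the table of TEAEs leading to treatment discontinuation (SAP 9.3.2), and the reporting limit of 3 working days for non-serious events that require discontinuation, laboratory abnormalities included (Protocol 6.13.3).

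**Working it through.** No sample size, power or event figure is at issue, so the check is a comparison of the rules case by case.

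| Case | 6.13.2 | 6.13.10, repeat-test paragraph | 6.13.10, hepatotoxicity list | Result |
|---|---|---|---|---|
| (a) ALT or AST above 3 and up to 8 x ULN, no other criterion, neither confirmed nor worsening | Laboratory AE | Reporting and stopping conditions not met | Not met | Conflict on AE status |
| (b) As (a), but confirmed, or worsening without reaching a listed criterion | Laboratory AE | Laboratory AE; stop | Not met | AE status agrees; permanence of the stop not stated |
| (c) First ALT or AST above 8 x ULN, repeat pending or not confirmed | Laboratory AE | Repeat; stop and report if confirmed or worsening | AE; permanent discontinuation; confirmation not mentioned | The two parts of 6.13.10 overlap; order not stated |
| (d) First ALT or AST above 3 x ULN with the bilirubin, INR or symptom criterion | Laboratory AE | As (c) | As (c) | As (c) |
| (e) Bilirubin alone above 3 x ULN | Laboratory AE | Covers enzymes only | Not met | No conflict |

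Case (a) is the direct conflict. It turns on the condition in 6.13.10 that the event "should be reported as a laboratory AE within the CRF if the enzyme elevation is confirmed or worsening", which 6.13.2 does not contain. Cases (c) and (d) arise because the repeat-test rule applies to every ALT or AST above 3 x ULN, and so includes values that already meet the hepatotoxicity list. On permanence, Protocol 6.13.12 shows that the protocol can be explicit: it says product may be resumed once a subject with ketoacidosis has stabilised. 6.13.10 has no equivalent statement for a confirmed isolated elevation.

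The next question is whether other planned outputs would recover an unlogged elevation.
- SAP 9.4 classifies laboratory values as low, normal or high against the reference range and plans shift tables for selected parameters. In such a table a value just above the ULN and a value of 9 x ULN are both high.
- The serum chemistry tables in the SAP index (14.3.4.3 and 14.3.4.4) are results and changes by visit, and shifts.
- SAP 9.4 mentions tables of maximum grade or toxicity, but none is indexed.
- Individual values appear in Listing 16.2.8.2.

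So the values are kept, but no indexed table counts subjects above 3 x or 8 x ULN, or with the combined enzyme and bilirubin criterion.

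**The case against.** The strongest defence is that 6.13.10 is a two-tier rule. Any ALT or AST above 3 x ULN is repeated, with a stop if confirmed or worsening; where a hepatotoxicity criterion is met, discontinuation is permanent. This reading is plausible and it limits the point. A reader might infer that the protocol contradicts itself on whether product stops before or after confirmation. The documents do not support that: 6.13.2 has no stopping rule, and nothing in 6.13.10 tells a site to keep dosing a subject who already meets a hepatotoxicity criterion. For the same reason, the 2 to 3 daily doses that fall in a 48 to 72 hour wait are not a consequence the protocol prescribes. What remains is an unstated order and an unstated permanence.

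Three other inferences also fail.
- A confirmed, symptom-free elevation that is stopped but not permanently discontinued is what a two-tier rule produces, not an inconsistency.
- The absence of INR from Table 1 is not a defect, because 6.13.10 asks for additional tests once AST or ALT exceeds 3 x ULN.
- The hepatotoxicity diagnosis does not have two definitions. There is one list; only the need for confirmation is left open.

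On AE status, one could read the 6.13.10 condition as sufficient rather than necessary, so that both rules hold and every value above 3 x ULN is logged. The condition would then do no work for reporting, and a site reading 6.13.10 alone would not reach that result. The conflict stands.

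On counts, it is fair to say that an isolated unconfirmed value between 3 and 8 x ULN is not hepatotoxicity under the protocol's list. Whether its preferred term would be counted depends on a term list that is not in the documents. Investigators are blinded, so uneven logging need not favour an arm. These objections rule out any claim of demonstrated bias. They do not make the log a consistent source.

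**Conclusion.** The point holds in limited form. Protocol 6.13.2 and 6.13.10 conflict on whether a single unconfirmed ALT or AST above 3 x ULN is a laboratory AE. Within 6.13.10, the order of repeat testing and permanent discontinuation, and the permanence of the first-tier stop, are ambiguous rather than contradictory. Because the special-interest count comes only from preferred terms in the AE log, and no indexed table applies the ULN criteria, hepatic AE reporting can depend on the section a site follows.

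The size cannot be computed: the documents give neither a rate of unconfirmed elevations nor the preferred-term list. One subject is 1/140 = 0.7 percentage points of the planned bexagliflozin arm or 1/70 = 1.4 points of the planned placebo arm. That is the weight of one subject, not an estimate of the effect, and it matters for the hepatotoxicity count only if the term list would include the event. The HbA1c analysis model is not at issue.

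**What to change.** 1. Reconcile Protocol 6.13.2 and 6.13.10 so that one statement says whether an unconfirmed ALT or AST above 3 x ULN is a laboratory AE.
2. In 6.13.10, state how the repeat test and permanent discontinuation are ordered when a first value already meets a hepatotoxicity criterion, and whether the stop for a confirmed isolated elevation is temporary or permanent. The thresholds and actions are for the sponsor's medical team.
3. In the SAP, add a by-arm table of subjects meeting the protocol's hepatic laboratory criteria, derived from central-laboratory values: ALT or AST above 3 x ULN, ALT or AST above 8 x ULN, ALT or AST above 3 x ULN with total bilirubin above 2 x ULN, and bilirubin above 3 x ULN. Show it beside the preferred-term count, not in its place. The INR and symptom criteria cannot be derived from these three tests and would still rely on AE reporting.

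The cost is one protocol clarification and one additional table from data already collected. The table does not depend on whether a site logged the event.
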